- 1b) to prospectively assess the potential clinical impact of HRME on the diagnosis and endoscopic surveillance of BE-associated neoplasia by determining if HRME alters the decision to obtain a mucosal biopsy or perform endoscopic mucosal resection (EMR) and changes the total number of total mucosal biopsies taken per procedure;
- 2) to determine the diagnostic accuracy (sensitivity, specificity, positive predictive value, negative predictive value) of HRME for the in-vivo diagnosis of neoplasia in a surveillance population of patients with BE using histopathologic diagnosis of mucosal biopsies as the reference standard;
- 3) to compare the total procedure time for imaging and mucosal biopsy acquisition of HRME with WL, stratified by length of BE (less than 3 cm and greater than 3 cm) and to determine the average HRME imaging time.

Section E: Protocol Risks/Subjects

E1. Risk Category

Category 3: Research involving greater than minimal risk and no prospect of direct benefit to the individual subject, but likely to yield generalizable knowledge about the subject's disorder or condition.

E2. Subjects

Gender:

Both

Age:

Adult (18-64 yrs)

Ethnicity:

All Ethnicities

Primary Language:

English

Groups to be recruited will include:

Patients

Which if any of the following vulnerable populations will be recruited as subjects?

Vulnerable populations require special protections. How will you obtain informed consent, protect subject confidentiality, and prevent undue coercion?

E3. Pregnant woman/fetus

Will pregnant women and/or fetuses (as described in 45 CFR 46 Subpart B) be enrolled in the research?

No

E4. Neonates

Will neonates of uncertain viability or nonviable neonates (as described in 45 CFR 46 Subpart B) be enrolled in the research?

No

E5. Children

Will children be enrolled in the research?

No

Section F: Design/Procedure

F1. Design

Select one category that most adequately describes your research:

u) Drug, Phase II, Single Center

Discuss the research design including but not limited to such issues as: probability of group assignment, potential for subject to be randomized to placebo group, use of control subjects, etc.

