The patient will be assigned to one of two groups: Group A: high resolution white-light endoscopy followed by random biopsy (WL) or Group B: high resolution white-light endoscopy plus HRME followed by directed mucosal biopsy (HRME). Randomization assignments (WL vs. HRME) will be computer-generated with allocation concealment using sealed envelopes.

Inclusion Criteria:

All consecutive outpatients with > 1 cm biopsy-proven Barrett's Esophagus who are undergoing standard of care endoscopic surveillance for metaplasia, dysplasia, or neoplasia.

Exclusion Criteria:

- Allergy or prior reaction to the fluorescent contrast agent proflavine
- Patients who are unable to give informed consent
- Known advanced adenocarcinoma of the distal esophagus, or dysplastic/suspected malignant esophageal lesion greater than 2 cm in size not amenable to EMR
- Patients with a history of a severe allergic reaction (anaphylaxis)
- Patients unable to undergo routine endoscopy with biopsy
- Women who are pregnant or breastfeeding
- Prothrombin time greater than 50% of control; PTT greater than 50 sec, or INR greater than 2.0
- Inability to tolerate sedated upper endoscopy due to cardiopulmonary instability or other
- Patients with known, untreated esophageal strictures, prior partial esophageal resection, or altered anatomy preventing passage of the endomicroscope
- Patients with known severe esophagitis
- Patients with suspected but no biopsy confirmed BE

F2. Procedure

Written informed consent will be obtained prior to study participation using the IRB-approved consent form. Identifying information collected includes D.O.B., age, gender, race and date of encounter. The patient will be assigned to one of two groups: Group A: high resolution white-light endoscopy followed by random biopsy (WL) or Group B: high resolution white-light endoscopy plus HRME followed by directed mucosal biopsy (HRME). Randomization assignments (WL vs. HRME) will be computer-generated with allocation concealment using sealed envelopes.

White Light Endoscopy (WL) Procedure (Group A)

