Patients assigned to the WL group will undergo careful standard examination of the upper GI tract with a standard high resolution endoscope (Olympus Corporation) without HRME. Endoscopic landmarks and BE characteristics will be described as listed in the previous section. Any mucosal lesions in the BE will be classified using the Paris classification. The endoscopist will predict whether BE and dysplasia are present based upon the white light endoscopic findings (endoscopic diagnosis) and whether neoplasia is suspected if there are any endoscopic lesions (endoscopic plan).

Mucosal biopsies of any discrete lesions will be obtained and placed in separate pathology containers per standard of care. Then, four-quadrant mucosal biopsies of the flat BE mucosa (a biopsy from each quadrant of the BE at each level) will be taken per standard of care: every 1 cm (for patients with suspected neoplasia) or every 2 cm (for patients undergoing routine surveillance), starting at the GE junction, moving proximally to the squamocolumnar junction. These mucosal biopsies will be obtained in a similar fashion to the standard Seattle biopsy protocol⁴. This biopsy protocol is commonly used for obtaining surveillance biopsies to sample representative areas of the entire length of the BE. Each level of the biopsies designated by the distance (in centimeters) on the endoscope from the patient's gums.

The total time of the procedure, as well as the time needed to complete the standard endoscopy and the time needed to take tissue biopsies, will be recorded. The co-investigator or research coordinator will indicate the biopsy number and location of the biopsy on a standardized BE map. The biopsies from each site will be placed in formalin and labeled according to the biopsy location.

Post-procedure, the endoscopist will inspect the map created by the coordinator and approve the data recorded. The number of biopsies obtained and biopsy specimen bottles sent for processing will be tracked to allow calculation of pathology costs.

High Resolution Microendoscopy (HRME) Procedure (Group B)

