All patients who fit the study criteria will be consented for HRME with biopsy and possible EMR (similar to colonoscopy with possible polypectomy). Examination of the esophagus, stomach, and small intestine with standard endoscopy will be performed using a high resolution video endoscopy (Olympus). The level of the gastroesophageal (GE) junction will be recorded. The level of the squamo-columnar junction (Z line) will also be recorded. Any proximal displacement of the Z line or gap between the GE junction and Z line will normally raise the suspicion for BE due to the presence of columnar mucosa in the distal esophagus. The maximum length of suspected BE (i.e. distance between the GE junction and Z line) and pattern of the BE (islands, tongues, circumferential columnar epithelium) will be recorded and photographed. A description of the BE using the Prague C&M criteria, which is used to describe the maximal length of BE and extent of circumferential BE, will also be recorded {Sharma, 2006 #4178}. Esophagitis will be described using the Los Angeles classification. The size, morphology, and location in the esophagus of every macroscopically visible lesion will be recorded and described using the 2002 Paris Endoscopic Classification of neoplastic lesions. The height of the mucosal lesion will be assessed by comparison with the diameter of a closed biopsy forceps (2.5 mm) {, 2003 #4280}.

After the endoscopic examination, the endoscopist will provide an endoscopic diagnosis for any visible mucosal lesions (pre-HRME diagnosis: i.e. neoplastic vs. non-neoplastic) and a plan for management during the procedure, such as biopsy or endoscopic mucosal resection (pre-HRME plan). These will be recorded prior to the initiation of HRME imaging.

For the HRME portion of the exam, 5-10 ml of proflavine hemisulfate (0.01%) will be sprayed on the esophageal mucosa. Proflavine is being used under an IND from the FDA (#102217). The HRME itself is an IDE exempt device per the FDA. The HRME will then be inserted through the biopsy channel of the endoscope and gently placed against the mucosa. The endoscopist will image each WL-discrete lesion first from the most distal to the most proximal. For each HRME imaged site, an optical read will be obtained (neoplastic vs. non-neoplastic) followed by a tissue biopsy of the imaged areas.

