Section G: Sample Size/Data Analysis

G1. Sample Size

How many subjects (or specimens, or charts) will be used in this study?

Local: 47 Worldwide: 100

Please indicate why you chose the sample size proposed:

Approximately 100 subjects with 50 in the WL-arm and 50 in the HRME-arm. We anticipate that 15-20% of subjects may be not complete their endoscopy for various reasons (lack of biopsies, loss of Barrett's mucosa, visualization of a lesion > 2 cm, inability to complete endoscopy, etc.) which would allow 40 in each arm. Since each patient only requires one visit for enrollment into the study, we expect that 80 patients will be enrolled and randomized and complete the study.

G2. Data Analysis

Provide a description of your plan for data analysis. State the types of comparisons you plan (e.g. comparison of means, comparison of proportions, regressions, analysis of variance). Which is the PRIMARY comparison/analysis? How will the analyses proposed relate to the primary purposes of your study?

In this trial, the randomization will be stratified by risk group: high risk and average risk. All analyses described below will be stratified as well.

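### Aim 3's two length strata leave a Barrett's length of exactly 3 cm unassigned; place it in advance and adjust the procedure-time comparison for recorded length

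*Protocol*

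**What the plan says.** The third aim in Section D of the protocol is "to compare the total procedure time for imaging and mucosal biopsy acquisition of HRME with WL", and this comparison is to be "stratified by length of BE (less than 3 cm and greater than 3 cm". The same aim also sets out "to determine the average HRME imaging time". This is the only place where a 3 cm cut appears.

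Three other parts of the documents bear on it:

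- **Eligibility (protocol, Section F1).** The trial takes "All consecutive outpatients with > 1 cm biopsy-proven Barrett's Esophagus". No upper limit on length is given.
- **Measurement (protocol, Section F2).** Under the HRME procedure, "The maximum length of suspected BE (i.e. distance between the GE junction and Z line" is defined and recorded during the white-light examination, before HRME imaging begins. No precision or rounding rule is stated. Under the WL procedure, biopsy levels are "designated by the distance (in centimeters) on the endoscope".
- **Analysis (protocol Section G2 and SAP).** "In this trial, the randomization will be stratified by risk group: high risk and average risk". The analyses described there are stratified the same way. They cover diagnostic yield and specificity. There is no procedure-time analysis and no use of length.

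**The concern.** A stratification rule should place every eligible patient in exactly one stratum, and this one has a gap at a value that may well occur. An analyst who applies it literally has nowhere to put a 3 cm patient and finds no guidance elsewhere. If the question is settled only once the times have been seen, the choice of side is no longer independent of the result.

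The second matter is efficiency. Length largely determines how many biopsy levels are taken, and in the HRME arm each flat-mucosa biopsy is preceded by an optical read. Procedure time should therefore rise with length in both arms. Two broad strata use only part of that information. Because length is not a randomisation stratum, the arms may differ in length by chance within each stratum. The background section presents shorter procedures as one of the hoped-for benefits of HRME, so the time comparison deserves a complete and reasonably precise analysis.

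**Working it through.** The documents give no sample size, power, significance level or standard deviation for procedure time, so Aim 3 has no planned figure to reproduce. The check is logical, with two short calculations to show scale.

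**1. Does the rule cover every eligible length?** Eligible lengths L satisfy L > 1 cm. The strata are L < 3 and L > 3.

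- 1.5, 2, 2.5 and 2.9 cm fall in the lower stratum.
- 3.1, 3.5, 4 and 5 cm fall in the upper stratum.
- 3.0 cm falls in neither.

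If either limit is made inclusive (< 3 with ≥ 3, or ≤ 3 with > 3), every eligible length falls in exactly one stratum.

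**2. How many patients could this touch?** The base is the SAP's own expectation: "we expect that 80 patients will be enrolled and randomized and complete the study". That figure follows from 100 randomised with 20% loss: 100 × (1 − 0.20) = 80, or 50 × 0.80 = 40 per arm. The share with exactly 3 cm is not in the documents, so a range is assumed:

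| Assumed share at 3 cm | Patients out of 80 |
|---|---|
| 2% | 0.02 × 80 = 1.6, about 2 |
| 5% | 0.05 × 80 = 4 |
| 10% | 0.10 × 80 = 8 |
| 20% | 0.20 × 80 = 16 |

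The upper part of the range is more likely if lengths are recorded in whole centimetres, and the lower part if they are recorded more finely. The documents do not say which applies.

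**3. How much does workload vary inside one stratum?** Assume 2 cm spacing, fully circumferential BE, and a four-quadrant set at both ends of the segment. The count of flat-mucosa biopsies is then 4 × (L/2 + 1):

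- L = 4 cm: 4 × (2 + 1) = 12
- L = 10 cm: 4 × (5 + 1) = 24

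If no set is taken at the upper end, the count is 4 × L/2, giving 8 and 20. The 10 cm value is only an example of a long segment. Patients on 1 cm spacing have more levels, and islands or tongues would give fewer biopsies. Either way, the number of levels rises with length within the upper stratum, in steps set by the spacing.

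**4. Is length usable as a covariate?** In the HRME arm it is recorded before imaging starts. The WL text refers to a list of landmarks and BE characteristics given elsewhere; I take this to be the list under the HRME procedure, which includes length. On that reading, length is available in both arms without new data.

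**The case against.** A reader might infer that patients with 3 cm are dropped from the procedure-time comparison. The documents do not support that. Aim 3 is one line in a statement of objectives, no section excludes these patients from anything, and an unstratified comparison or the average HRME imaging time would include them. What is established is that they have no stratum.

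A reader might also infer that the coarse strata bias the comparison. They do not: in a randomised trial, leftover length differences within strata are chance imbalance. The case for adjustment is precision.

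Several further objections are fair:

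- Whole-centimetre recording is an inference. The centimetre wording describes biopsy levels, while the definition of BE length states no rounding. A recorded 3 cm is plausible, but its frequency is unknown.
- Showing results for short and long segments is a legitimate objective, and nothing in the plan forbids adjusting for length as well.
- The documents do not indicate which side 3 cm belongs on, or that time needs a log scale.
- An analyst would probably settle the boundary sensibly without being told.

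These points limit the size of the concern. They do not close the gap, and they do not count against adjusting for a variable that is already recorded and plainly related to the outcome.

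**Conclusion.** The point holds in a limited form. The Aim 3 strata are incomplete at exactly 3 cm, such a patient is eligible, and neither the protocol nor the SAP assigns the value. The number affected is unknown: about 2 to 16 of 80 under an assumed share of 2% to 20%. The gap does not affect the primary diagnostic-yield analysis, the randomisation strata or the sample size, and it is not evidence that any patient will be excluded.

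The more useful part of the point is the method. Covariate adjustment for length in centimetres, together with the risk group used in randomisation, makes better use of the data than two strata with a hole between them. The gain cannot be quantified, because the documents give no variance for procedure time and no correlation of time with length. It rests on the reasoning that more levels mean more time, and on length being recorded in both arms. The priority is low: desirable and cheap.

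**What to change.** Before analysis:

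1. Reword Aim 3 so that one stratum includes 3 cm, for example less than 3 cm and 3 cm or more. Either side will do if it is fixed in advance.
2. State the precision to which BE length is recorded and how it is rounded, and confirm that it is recorded in both arms.
3. Add an Aim 3 paragraph to the SAP. The main comparison is a regression of procedure time on arm, adjusted for the randomisation risk group and for recorded BE length in centimetres. A log scale for time is optional, but the choice should be made in advance.
4. Keep the two length strata as a descriptive display of procedure time by arm, so that readers still see short and long segments separately.

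The cost is one changed phrase in the protocol and a short new paragraph in the SAP, which has no Aim 3 text to amend, plus a little analysis work. It needs no change to procedures or sample size, and no measurement beyond the procedure times that Aim 3 already requires and the recorded length.

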Following the targeted biopsies, random four-quadrant biopsies of the flat BE mucosa will be taken with every 1 cm (for patients with suspected high grade dysplasia (HGD)) or every 2 cm (for patients undergoing routine surveillance), starting at the GE junction, moving proximally to the Z line per standard of care. Prior to the standard tissue biopsy, an HRME read will be obtained from the area (neoplastic vs. non-neoplastic). A superficial dimple will be made with the HRME of each imaged site to "mark" the imaged area for biopsy. The latter is commonly performed in imaging correlation studies and has not been shown to affect pathology.

Pathology

The fixed biopsies will be oriented/embedded in paraffin and sectioned to facilitate comparison between histology and HRME images. Afterwards the serial sections will be routinely stained with hematoxylin and eosin for histopathologic examination.

The biopsies or resected specimens (from EMR) obtained from the examined areas will be routinely processed and interpreted by a single expert gastrointestinal pathologist in a blinded fashion and graded according to the Vienna Classification. The pathologist will provide a diagnosis for each biopsy specimen in the cassette to allow correlation with the endoscopic and HRME findings. The histopathologic diagnosis for each biopsy will be recorded on a standardized data collection form.

Section G: Sample Size/Data Analysis

G1. Sample Size

How many subjects (or specimens, or charts) will be used in this study?

Local: 47 Worldwide: 100

Please indicate why you chose the sample size proposed:

Approximately 100 subjects with 50 in the WL-arm and 50 in the HRME-arm. We anticipate that 15-20% of subjects may be not complete their endoscopy for various reasons (lack of biopsies, loss of Barrett's mucosa, visualization of a lesion > 2 cm, inability to complete endoscopy, etc.) which would allow 40 in each arm. Since each patient only requires one visit for enrollment into the study, we expect that 80 patients will be enrolled and randomized and complete the study.

G2. Data Analysis

Provide a description of your plan for data analysis. State the types of comparisons you plan (e.g. comparison of means, comparison of proportions, regressions, analysis of variance). Which is the PRIMARY comparison/analysis? How will the analyses proposed relate to the primary purposes of your study?

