In this trial, the randomization will be stratified by risk group: high risk and average risk. All analyses described below will be stratified as well.

The primary outcome of the randomized trial is Diagnostic Yield, defined as the proportion of all biopsies that are truly neoplasia after histopathological review. A generalized linear model for logistic regression with multiple correlated binary outcomes within each patient will be used for data analysis (McCullagh and Nelder, 1989). In this model the binary outcome for each biopsy specimen is whether the specimen is classified as neoplasia or non-neoplasia, and the explanatory variable is the biopsy protocol group (Group A is standard of care, the control group; Group B is the optical biopsy protocol with HRME). PROC GLIMMIX in SAS will be used because of the correlations among samples from the same patient. The model will allow for testing whether the proportion of samples classified as neoplasia differs between the two biopsy protocols. The analysis will be stratified by risk group --- High Risk and Average Risk. A secondary outcome will be the estimation of the accuracy of each biopsy protocol. Because of the small numbers of true neoplasia patients that are expected to be present among patients enrolled in the trial, sensitivity on a patient-basis will not be estimated. However, specificity will be estimated, stratified by risk group, for each of the two biopsy protocols, along with a one-sided 95% confidence interval

Section H: Potential Risks/Discomforts

H1. Potential Risks/Discomforts

Describe and assess any potential risks/discomforts; (physical, psychological, social, legal, or other) and assess the likelihood and seriousness of such risks:

Possible risks associated with the study procedures are listed below. There may also be risks that are not known. Many side effects go away soon after the procedure, but in some cases, side effects may be serious, long-lasting or permanent, and may even cause death. It is important that the participant tell the study staff about any side effects that he/she may have had even if he/she does not think it is related to the procedure.

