The primary outcome of the randomized trial is Diagnostic Yield, defined as the proportion of all biopsies that are truly neoplasia after histopathological review. A generalized linear model for logistic regression with multiple correlated binary outcomes within each patient will be used for data analysis (McCullagh and Nelder, 1989). In this model the binary outcome for each biopsy specimen is whether the specimen is classified as neoplasia or non-neoplasia, and the explanatory variable is the biopsy protocol group (Group A is standard of care, the control group; Group B is the optical biopsy protocol with HRME). PROC GLIMMIX in SAS will be used because of the correlations among samples from the same patient. The model will allow for testing whether the proportion of samples classified as neoplasia differs between the two biopsy protocols. The analysis will be stratified by risk group --- High Risk and Average Risk. A secondary outcome will be the estimation of the accuracy of each biopsy protocol. Because of the small numbers of true neoplasia patients that are expected to be present among patients enrolled in the trial, sensitivity on a patient-basis will not be estimated. However, specificity will be estimated, stratified by risk group, for each of the two biopsy protocols, along with a one-sided 95% confidence interval

Section H: Potential Risks/Discomforts

H1. Potential Risks/Discomforts

Describe and assess any potential risks/discomforts; (physical, psychological, social, legal, or other) and assess the likelihood and seriousness of such risks:

Possible risks associated with the study procedures are listed below. There may also be risks that are not known. Many side effects go away soon after the procedure, but in some cases, side effects may be serious, long-lasting or permanent, and may even cause death. It is important that the participant tell the study staff about any side effects that he/she may have had even if he/she does not think it is related to the procedure.

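### G1 places 53 of 100 patients outside the local site while F1 says single centre, and site is in neither the randomisation strata nor the primary model: a modest, cheaply recovered loss of precision.

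*Protocol*

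**What the plan says.** Protocol F1 (Design) selects the category "u) Drug, Phase II, Single Center". Protocol J2 has subjects coming from the investigator's own practice. G1 (Sample Size), identical in protocol and SAP, states "Local: 47 Worldwide: 100" and then "Approximately 100 subjects with 50 in the WL-arm and 50 in the HRME-arm". It adds "We anticipate that 15-20% of subjects may be not complete their endoscopy for various reasons", "which would allow 40 in each arm".

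G2 (Data Analysis) says that "the randomization will be stratified by risk group: high risk and average risk" and that the analyses are stratified in the same way. For the primary outcome, the proportion of biopsies that prove neoplastic, "the explanatory variable is the biopsy protocol group". The model is fitted in PROC GLIMMIX to allow for correlation between samples from one patient. F1 and F2 describe computer-generated assignments in sealed envelopes. They do not say whether lists or envelopes are prepared by site.

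Site is therefore named neither as a randomisation stratum nor as a fixed or random term in the primary model. The documents do not say where the patients outside the local site are enrolled, or at how many sites.

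**The concern.** F1 and G1 cannot both describe the whole trial. If about half the patients come from elsewhere, site is a plausible source of variation in this endpoint. Yield has biopsies in both numerator and denominator. Lesion recognition and the HRME read are made by the endoscopist, and the spacing of flat-mucosa biopsies (1 cm or 2 cm) depends on what is suspected, so the denominator can differ by operator and by case mix.

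If sites differ in yield and the list ignores site, the arms can by chance contain different shares of each site, and part of the site difference then appears in the arm comparison. If the list does respect site but the model does not, the standard error keeps variation that the design has already removed. Either way some precision is lost, in a trial for which the plan states no effect size, alpha or power.

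**Working it through.** **1. The plan's own arithmetic.** 50 × (1 − 0.20) = 40 per arm, 80 in total, so the stated figure reproduces at 20% non-completion. At 15% it would be 42.5 per arm. Patients outside the local site: 100 − 47 = 53.

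**2. Chance imbalance in site share, list not stratified by site.**
- N = 100, 47 local: SD = √(0.47 × 0.53 × (1/50 + 1/50)) = 0.0998. The exact hypergeometric value is 0.1003.
- N = 80, 38 local (assumed pro rata: 0.47 × 80 = 37.6): √(0.475 × 0.525 × (1/40 + 1/40)) = 0.1117. The exact value is 0.1124.
- Exact probability of an imbalance of at least 10 points: 42% (N = 100) and 50% (N = 80). Of at least 20 points: 4.5% and 11.7%.

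**3. Shift in the arm difference.** 95% range = 1.96 × SD × gap in yield between sites. The gap is assumed.

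| Assumed gap | N = 100 | N = 80 |
|---|---|---|
| 5 points | ±1.0 | ±1.1 |
| 10 points | ±2.0 | ±2.2 |
| 15 points | ±2.9 | ±3.3 |

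**4. Yardstick.** Assume a 10% yield, 12 biopsies per patient and intra-patient correlation 0.2 to 0.4. The variance of a patient's yield is 0.10 × 0.90 × (1 + 11 × 0.2)/12 = 0.0240, or 0.0405 at correlation 0.4. The SE of the arm difference at 50 per arm is √(0.04 × 0.0240) = 3.1 points, or √(0.04 × 0.0405) = 4.0 points. The site component has SD 0.10 × 10 = 1.0 point for a 10-point gap, which is 0.0001/0.00162 to 0.0001/0.00096, or about 6 to 10% of the variance. For a 5-point gap it is about 2 to 3%; for 15 points, 0.000225/0.00162 to 0.000225/0.00096, about 14 to 23%.

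**5. Simulation.** This is illustrative: a linear model on patient-level yields rather than GLIMMIX, two sites, N = 80 with 38 local, 12 biopsies per patient, correlation 0.2 or 0.4, two-sided 5% level, no risk strata, 8,000 runs per scenario. Site yields were 5% against 10%, 15% or 25%.
- List not stratified by site: the mean shift is about zero, and type I error without a site term is 4.4 to 4.9%.
- In runs where the local share was at least 15 points higher in one arm, the unadjusted estimate moved on average by about 0.9 points (5-point gap), 1.7 to 1.8 (10-point gap) or 3.6 (20-point gap). With a site term it moved by at most 0.15.
- Precision at a 10-point gap: adding site lowers the SD of the estimate from 3.63 to 3.48 points (correlation 0.2) or from 4.65 to 4.54 (correlation 0.4).
- List balanced by site, site left out of the model: type I error is 2.5 to 4.7%, against 4.2 to 5.3% with site included. The lowest values, 2.5 and 3.3%, come from the 20-point gap; at 10 points they are 4.2 and 4.5%.

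**The case against.** F1 is a pick-one field on a local review-board form and may describe only the local part of the trial. The opening of the form is not in the public copy and may list other institutions. That stands: the label alone is a clerical matter, though F1 still has to be squared with G1.

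A reader might infer that H3 also contradicts G1. It does not. H3 asks only whether the local institution acts as sponsor-investigator or coordinating centre, and a negative answer fits a multi-site trial coordinated elsewhere. H3 needs no change.

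A reader might also infer that ignoring site biases the result. Patients are randomised, the shift averages zero, and the unadjusted test holds its level in the simulation. Chance imbalance is ordinary sampling variation that patient-level standard errors already cover. This objection stands in full against any claim of systematic bias. What remains is the shift conditional on the imbalance that actually occurs, and the avoidable variance.

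It is also tempting to say that envelopes must be held at each site. No document says so. If they are, and the list is balanced by site, the imbalance calculation does not apply and the issue becomes a possibly conservative test.

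Risk-group stratification and one blinded pathologist absorb some site differences, but not differences in endoscopist or biopsy practice. Finally, the plan expects few patients with true neoplasia, so extra model terms could be unstable. That is a fair limit on the remedy.

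**Conclusion.** The point holds as a cheap improvement. F1 and G1 disagree, and site is absent from both randomisation and the primary model. Under an assumed 10-point gap between sites (range 5 to 15), chance imbalance contributes a shift with a 95% range of about ±2 points (±1 to ±3). These are 95% ranges, not maxima. Against an SE of 3.1 to 4.0 points, itself resting on assumed yield, biopsy count and correlation, this is a minor share of the variance at gaps of 5 to 10 points and a larger one at 15.

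The documents do not support a finding of systematic bias or of inflated type I error. No site gap or expected yield is given in them, so the size is conditional on the assumptions shown.

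**What to change.** 1. Reconcile F1 with G1: state that patients are enrolled outside the local site, at how many sites, and how envelopes are prepared and held. Leave H3 as it is.
2. Generate the randomisation list by site within risk group.
3. Add one local/other site term to the primary GLIMMIX model, keeping the planned risk-group stratification. Prespecify that, if neoplastic events are too sparse for a stable fit, the site-adjusted model is reported as a sensitivity analysis.

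The cost is wording in the protocol and SAP, one degree of freedom, and at least four site-by-risk cells for 100 patients, some of them small. No extra patients are needed.

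### Minor, wrong as written: the prothrombin-time exclusion is met by a normal result and should be reworded as more than 50% above control

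*Protocol*

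**What the plan says.** One line of the exclusion criteria in Protocol Section F1 deals with clotting: "Prothrombin time greater than 50% of control; PTT greater than 50 sec, or INR greater than 2.0". Its three parts are joined as alternatives, so any one of them is enough to exclude.

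The protocol does not define the control value and does not say whether the prothrombin time is measured in seconds or as percent activity. Nothing else in the protocol restates or corrects the limit. The SAP reproduces only Section G and part of Section H and contains no eligibility text.

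Three other features of the protocol bear on the point:

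- **Population.** Section F1 recruits "All consecutive outpatients with > 1 cm biopsy-proven Barrett's Esophagus who are undergoing standard of care endoscopic surveillance". A separate exclusion covers "Patients unable to undergo routine endoscopy with biopsy".
- **Testing.** Sections F1 and F2 schedule no coagulation test. Section N answers the blood-draw question as not applicable and says that no sample is taken purely for research.
- **Screening.** Sections J1 and J2 provide for chart screening before patients are approached. The health-record information covered by the J1 waiver includes laboratory findings. A GI physician approves eligible subjects before they are telephoned.

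**The concern.** A limit meant to keep out patients who bleed easily should be crossed only by abnormal results. This one is crossed by a normal result. Any patient with an ordinary prothrombin time in the chart meets an exclusion criterion on the plain text, and enrolling that patient departs from the approved protocol.

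The line has a plausible safety purpose. Group B patients have multiple biopsies and possible mucosal resection (Section F2), and bleeding is a listed biopsy risk (Section H1). Staff who check eligibility should not have to guess where the limit lies. The direction can be inferred from the rest of the line, but the exact boundary cannot.

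**Working it through.** The plan gives no derived figure to reproduce here, so the check compares a normal result with the criterion under each possible reading.

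**Inputs.** From Protocol Section F1: prothrombin time above 50% of control, "PTT greater than 50 sec" and "INR greater than 2.0". Assumed, because the documents do not give them: a normal prothrombin time about equal to control (ratio about 1.0, or 100%); a control value of 12 s, range 11 to 13.5 s; an ISI between 1.0 and 2.0.

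**Step 1: reading in seconds.** The written cut-off is 0.5 × control; the probable intended cut-off is 1.5 × control.

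| Control (s) | As written, 0.5 × control (s) | More than 50% above control, 1.5 × control (s) |
|---|---|---|
| 11 | 5.5 | 16.5 |
| 12 | 6.0 | 18.0 |
| 13.5 | 6.75 | 20.25 |

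A normal value of about 12 s is above 6.0 s, so it is excluded as written. It is below 18.0 s, so it is eligible under the reworded clause. The conclusion needs only that a normal ratio of 1.0 exceeds 0.5 and does not exceed 1.5. It does not depend on the assumed seconds.

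**Step 2: reading as percent activity.** Normal activity is about 100%, and 100 > 50, so a normal patient is again excluded. Low activity is the abnormal direction, so here the inequality is reversed. The correct form would be activity below 50%, which a normal patient does not meet.

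**Step 3: consistency within the line.** The PTT and INR limits are upper limits on prolonged clotting. A prothrombin ratio just above 0.5 is not prolonged. The first limit therefore conflicts with its two neighbours, and the neighbours show the intended direction.

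**Step 4: can the clause simply be dropped?** INR = (prothrombin time ÷ control)^ISI. So a ratio of 1.5 corresponds to INR = 1.5^ISI, and INR 2.0 corresponds to a ratio of 2^(1/ISI).

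| ISI | INR at 1.5 × control | Ratio to control at INR 2.0 |
|---|---|---|
| 1.0 | 1.50 | 2.00 |
| 1.2 | 1.63 | 1.78 |
| 1.5 | 1.84 | 1.59 |
| 2.0 | 2.25 | 1.41 |

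The two limits coincide at ISI = ln 2 ÷ ln 1.5 = 0.693 ÷ 0.405 = 1.71. Below that, the INR limit alone is looser than 1.5 times control. At ISI 1.0 a patient with a ratio of 1.7 has INR 1.7. That patient is excluded by the reworded clause and eligible if the clause is deleted. Above 1.71 the INR limit is the stricter of the two.

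**The case against.** The strongest reply is that nobody running the trial would apply the clause literally, since it would turn away nearly every patient with a normal result. It reads naturally as shorthand for prolonged by more than half of control, and the rest of the line supports that. The approving GI physician would probably apply it that way, and patients who cannot have endoscopy with biopsy are excluded separately. The laboratory entry in Section J1 is a general privacy-form item. It permits access to results but does not show that anyone looks up clotting tests.

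All of this stands, and it is why the point is minor. It does not make the wording right: this is an operative eligibility rule, and good sense at the bedside does not alter the approved text.

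A reader might infer three stronger things that the documents do not support:

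- **A count of protocol deviations.** The documents do not say how many patients have a prothrombin time on file, so any assumed share would be invented. Scaling to the 100 worldwide would also extend this wording to sites whose text is not shown. Section G1 gives 47 as the local number, and in Section H3 the institution does not claim the sponsor-investigator or coordinating-center role.
- **Added danger to patients.** Read in seconds, the written clause is too strict: it also catches every prolonged result. Read as activity, it would miss low values, but the PTT and INR limits are correctly directed and still apply.
- **Damage to the comparison.** Nothing in the randomization, the sample size or the primary model uses this criterion.

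**Conclusion.** The criterion is wrong as written, and the point is minor. A normal prothrombin time meets the exclusion whether it is read in seconds or as percent activity, and no other text in the protocol or SAP corrects it. This rests on one assumption, that a normal result is about equal to control. The control values in seconds are illustrative.

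The effect is confined to eligibility checks for patients with a prothrombin time already on file. Their number is unknown. The warning against deletion is conditional: it holds for an ISI near 1, and more generally below about 1.71, and assumes that 1.5 times control was the intended limit.

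**What to change.** Ask the clinical investigators which measure was meant, then replace the prothrombin-time clause in Section F1 with one of these:

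- **If seconds were meant (the likelier reading):** prothrombin time more than 50% above control, that is, greater than 1.5 times control.
- **If percent activity was meant:** prothrombin activity less than 50% of control.

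Keep the PTT and INR limits as they are. Do not delete the clause by default. If the investigators are content with the INR limit alone, they should record that this may be looser than 1.5 times control.

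The cost is one line in a protocol amendment. Procedures, sample size and analysis do not change.
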